4.2. Scientific Rationale for Study Design

The population planned for this study will be healthy males and females of non-childbearing potential. Female participants will be confirmed not to be of childbearing potential because embryo-fetal development toxicity studies with PF-07328948 have not been conducted. In male participants, appropriate measures are expected to be followed to minimize potential transfer of PF-07328948 via semen to partners (see Appendix 4).

Because this is the first time PF-07328948 will be administered to humans, an escalating single, oral dose, crossover design is planned with careful assessment and ongoing review of safety, tolerability, and PK data of PF-07328948. Precautionary sentinel dosing will also be utilized in any period evaluating escalating doses of PF-07328948 to ensure that safety and tolerability data in a subset of 2 participants within each period supports testing additional participants in that period. In each period, approximately 6 participants are planned to receive PF-07328948, and approximately 2 participants are planned to receive placebo, with all the participants at the end of the study having received up to 4 doses of PF-07328948 and up to 2 placebo. The crossover design permits both within- and between-participants assessments of safety, tolerability, and PK at multiple dose levels and placebo.

In addition, the highest anticipated C_{max} and AUC_{24} of PF-07328948 will not exceed the pre-defined human exposure stopping limits nor exceed the highest feasible total daily dose Eurthermore, to permit an unbiased assessment of safety, the administration of both PF-07328948 and placebo in each period will be double-blinded to both site staff (except those involved in preparation of doses) as well as participants. To permit real-time review of the safety, tolerability, and PK data, a limited number of sponsor study team members will be unblinded.

CCI

. As a BDK inhibitor/degrader,

PF-07328948 is expected to inhibit BDK-mediated phosphorylation of BCKDH enzyme complex, resulting in an increase in BCAA/BCKA catabolism and a decrease in circulating BCAA and BCKA levels. As protein intake is known to impact plasma BCAA/BCKA levels, CCI

Lunch and dinner will be standardized when participants are confined in the CRU; additional efforts will be made to ensure lunch, dinner and snacks are as identical as is feasible on Day 1 for each period and on Day -1 where time-matched assessment is performed (Section 5.3.2).

CCI

Based on predicted half-life in human (~4 hours), PK samples were collected over 48 hours post-dose in Cohort 1. However, the preliminary PK data emerging from Cohort 1 suggested the terminal half-life could be longer than the predicted 4 hours therefore, participants in remaining Cohort 2 and optional Cohort 3 will be confined in CRU up to Day 4 with PK samples collected up to 72 hours post-dose. A washout interval of ≥ 7 days is proposed between doses within an individual participant; this interval should be sufficient based on all emergent PK data to date, and the projections that CCI levels return to baseline within approximately 72 hours post-dose based on a PK/PD model developed with preclinical data and emergent PK/PD data in Cohort 1. In addition, this washout interval should offer sufficient opportunity to review safety, tolerability, and PK data after each dosing period prior required for decision on the PF-07328948 dose to be evaluated in the subsequent period. However, sampling times, duration of sampling, and/or the length of the washout period may be modified and/or extended based on emerging PK and/or PD data. Participants may be asked to remain at the CRU after completion of Day 4 activities at the discretion of the investigator or if safety, tolerability, or PK data dictate the need to prolong inpatient stay in the CRU. The planned doses and assignment to study intervention in the escalation sequence (see Section 1.2) may be modified or repeated, as guided by emerging safety, tolerability, and PK data but will follow the dose-escalation rules defined in Section 6.6.1.

Decreased blood pressure was observed after single doses (≥ 20 mg/kg) of PF-07328948 in dogs in exploratory toxicology studies; however, no significant blood pressure changes were subsequently noted in GLP toxicology studies after single doses of ≤ 100 mg/kg in dogs. Serial triplicate assessment of blood pressure will be performed following single dose administration as outlined in SoA. Triplicate 12-lead ECGs and continuous cardiac telemetry

4.2.1. Choice of Contraception/Barrier Requirements

Human reproductive safety data are not available for PF-07328948. Therefore, the use of a highly effective method of contraception is required for male study participants and is recommended for partners of male study participants who are WOCBP (see Appendix 4).

4.2.2. Collection of Retained Research Samples

Retained Research Samples will be collected and stored for further analyses which may, for example, provide greater understanding of the study intervention.

4.3. Justification for Dose

The proposed dose levels of PF-07328948 were derived based on cumulative nonclinical data, including in vitro, in vivo, PK and PD data, and the completed nonclinical toxicity studies. Dose levels beyond the starting dose (in Period 1 of Cohort 1) may be modified based on emerging human safety, tolerability, and PK data in the current study.

4.3.2. Predicted Efficacious Concentration and Human Dose

The desired degree of target modulation is based on published human metabolomic data.^{3,4,7,8} As BCAAs are elevated ~20% on a population level in patients with cardiometabolic disease CCI

However, due to uncertainty around the degree of target modulation necessary for efficacy in patients with heart failure and the first-in-class nature of the mechanism of BDK inhibition, higher degrees of target modulation is desired to be evaluated if permitted by safety data.

4.3.3. Human Exposure Stopping Limits

The NOAELs in the pivotal 1-month GLP toxicity studies were which correspond to the highest doses tested in those respective studies.

Therefore, the human exposure stopping limits for PF-07328948 are based on unbound exposures at the NOAEL observed in the 1-month GLP toxicity study in rats which is defined as the most sensitive species.

- The human PF-07328948 C_{max} limit is CCI
- The human PF-07328948 AUC₂₄ limit is CCI

PFIZER CONFIDENTIAL

4.3.4. Rationale for Dose Selection

The safety, tolerability, and plasma PK of PF-07328948 after administration of single escalating oral doses across a wide dose/exposure range will be evaluated in this study. Dosing will occur in the fasted state, except in periods in which dosing may occur in the fed state to permit exploratory assessment of the effect of food on PF-07328948 PK and PD. The doses presented in Table 3 are projected based on nonclinical data and may be modified based on emerging human safety, tolerability, and PK data. Predicted human PK parameter estimates, toxicokinetic data, and projected efficacious concentrations were used to establish the initial range of planned doses in this study. The projected human exposures account for concentration-dependent protein binding within the planned dose range.

Table 3. Predicted Human Exposures, Pharmacodynamic Effects, and Safety Margin at Proposed Single Doses of PF-07328948

Dose (mg)	C _{ma} (ng/n		AU(ng.h	C ₂₄ ª /mL)	CO			F		F	
	Total	Free	Total	Free	CCI						6
10	461	1	2990	4	C						
30	1380	2	8910	11	C						
100	4610	6	29000	37	C						
300	13800	20	81500	112	C						
750	34600	64	181000	286	C						
1500	69200	173	310000	595	C						

- a. Human PK profiles were predicted using a 1-compartment model with the projected human PK parameters for PF-07328948 outlined in Section 4.3.1. Human plasma fu values were predicted using the linear equation (CCI and hepatic clearance was projected using the well-stirred model.
- b. Pharmacodynamic effects elucidated with Ile and KMV was simulated based on a PK/PD model developed with preclinical data and Ki for human BDK inhibition and human fasting plasma Ile and KMV baseline level. Ave reduction was calculated over 24 hours.
- c. SM, safety margin for unbound exposure (Cmax,u and AUC24,u) at the proposed doses were calculated based on the NOAELs in the 1-month GLP toxicity studies in both rats and dogs. The human exposure limits were defined as observed at NOAEL in rat 1-month GLP toxicity study.

The PF-07328948 starting dose level of 10 mg is planned. The predicted PF-07328948 C_{max,u} and AUC_{24,u} after single dose of 10 mg are below the exposure limits defined for PF-07328948 dose escalation in Section 4.3.3. The maximum reduction for plasma isoleucine and ketoisoleucine are predicted to be 3% and 4%, respectively, suggesting little target modulation at this dose. A single dose of 1500 mg (the top dose in Table 3) is estimated to provide an exposure margin respectively, relative to the exposure limits.

The dose range to be studied was selected to account for uncertainties in the projected $C_{\rm eff}$ and the projected therapeutic dose, while also bracketing the expected clinically effective dose range in humans for clinically relevant pharmacological activity and providing safety coverage for a wide range of PF-07328948 doses.

Assessment of the safety, tolerability, and PK after each single dose level will be conducted before escalating to the next dose level. The dose/exposure-escalation increments are planned to be up to approximately semi-logarithmic increases in exposure from the previous highest dose level that has been evaluated. If exposure exceeds the projected therapeutic range, or if changes in safety parameters are observed, smaller dose-escalation steps may be implemented.

The actual dose levels, target exposures, and/or dose level increments may be adjusted (higher or lower) during the study based on emerging human safety, tolerability, and PK data, but projected exposures will not exceed the predefined human exposure limits. If C_{max} -related adverse events are observed, split dosing (eg, the total dose will be divided into 2 or 3 parts on Day 1) may be used to potentially increase AUC without increasing C_{max} . Dose levels may also be repeated if warranted.

When the assessment of the effect of food on the PK and PD of PF-07328948 is conducted, the dose level will be selected based on emerging safety, tolerability, and PK data from previous periods of this study. The actual dose level used will be expected to achieve exposures similar to or greater than projected therapeutic exposures (as outlined in Section 4.3.2).

4.4. End of Study Definition

The end of the study is defined as the date of last scheduled procedure shown in the SoA for the last participant in the trial.

A participant is considered to have completed the study if they have completed all periods of the study, including the last scheduled procedure shown in the SoA.

5. STUDY POPULATION

This study can fulfill its objectives only if appropriate participants are enrolled, including participants across diverse and representative racial and ethnic backgrounds. Use of a prescreening tool is utilized for study recruitment purposes, it will include collection of information that reflects the enrollment of a diverse participant population including, where permitted under local regulations, age, sex, and race, and ethnicity. The following eligibility criteria are designed to select participants for whom participation in the study is considered appropriate. All relevant medical and nonmedical conditions should be taken into consideration when deciding whether a particular participant is suitable for this protocol.

Prospective approval of protocol deviations to recruitment and enrollment criteria, also known as protocol waivers or exemptions, is not permitted.

5.1. Inclusion Criteria

Participants are eligible to be included in the study only if all of the following criteria apply:

Age and Sex:

- 1. Female participants of non-child bearing potential and males must be 18 to 60 years of age, inclusive, at the time of signing the ICD.
 - Refer to Appendix 4 for reproductive criteria for male (Section 10.4.1) and female (Section 10.4.2) participants.
- 2. Female participants of non-child bearing potential and males who are overtly healthy as determined by medical evaluation including medical history, physical examination, laboratory tests, and cardiac monitoring.

Other Inclusion Criteria:

- 3. BMI of 17.5 to 30.5 kg/m²; and a total body weight >50 kg (110 lb).
- 4. Participants who are willing and able to comply with all scheduled visits, treatment plan, laboratory tests, lifestyle considerations, and other study procedures.
- 5. Capable of giving signed informed consent as described in Appendix 1, which includes compliance with the requirements and restrictions listed in the ICD and in this protocol.

5.2. Exclusion Criteria

Participants are excluded from the study if any of the following criteria apply:

Medical Conditions:

- 1. Evidence or history of clinically significant hematological, renal, endocrine, pulmonary, gastrointestinal, cardiovascular, hepatic, psychiatric, neurological, or allergic disease (including drug allergies, but excluding untreated, asymptomatic, seasonal allergies at the time of dosing).
 - Any condition possibly affecting drug absorption (eg, gastrectomy, cholecystectomy).
 - History of HIV infection, hepatitis B, or hepatitis C; positive testing for HIV, HBsAg, HBcAb, or HCVAb. Hepatitis B vaccination is allowed.
 - History of phototoxicity or photosensitivity.

2. Other medical or psychiatric condition including recent (within the past year) or active suicidal ideation/behavior or laboratory abnormality or other conditions or situations related to COVID-19 pandemic that may increase the risk of study participation or, in the investigator's judgment, make the participant inappropriate for the study.

Prior/Concomitant Therapy:

- 3. Use of prescription or nonprescription drugs and dietary and herbal supplements within 7 days or 5 half-lives (whichever is longer) prior to the first dose of study intervention through the last PK collection, with the exception of moderate/strong CYP3A inducers or time-dependent inhibitors which are prohibited within 14 days plus 5 half-lives prior to the first dose of study intervention. (Refer to Section 6.9 Prior and Concomitant Therapy for additional details).
- 4. Receipt of a COVID-19 vaccine within 7 days before screening or within 7 days before any visit in which a safety lab is planned. Vaccination with a COVID-19 vaccine that occurs greater than 7 days from either screening or any visit in which a safety lab is planned is permitted.

Prior/Concurrent Clinical Study Experience:

5. Previous administration with an investigational product (drug or vaccine) within 30 days (or as determined by the local requirement) or 5 half-lives preceding the first dose of study intervention used in this study (whichever is longer).

Diagnostic Assessments:

- 6. A positive urine drug test.
- 7. Screening supine BP ≥140 mm Hg (systolic) or ≥90 mm Hg (diastolic), following at least 5 minutes of supine rest. If BP is ≥140 mm Hg (systolic) or ≥90 mm Hg (diastolic), the BP should be repeated 2 more times and the average of the 3 BP values should be used to determine the participant's eligibility.
- 8. Renal impairment as defined by an eGFR <75 mL/min/1.73m² (based on serum creatinine). Based upon participant age at screening, eGFR is calculated from serum creatinine using the recommended CKD-EPI SCr formulas in Section 10.7.2 to determine eligibility and to provide a baseline to quantify any subsequent kidney safety events.
- 9. Standard 12-lead ECG that demonstrates clinically relevant abnormalities that may affect participant safety or interpretation of study results (eg, QTcF >450 ms, complete LBBB, signs of an acute or indeterminate- age myocardial infarction, ST-T interval changes suggestive of myocardial ischemia, second- or third-degree AV block, or serious bradyarrhythmias or tachyarrhythmias). If the uncorrected QT

interval is >450 ms, this interval should be rate-corrected using the Fridericia method only and the resulting QTcF should be used for decision making and reporting. If QTcF exceeds 450 ms, or QRS exceeds 120 ms, the ECG should be repeated twice and the average of the 3 QTcF or QRS values used to determine the participant's eligibility. Computer-interpreted ECGs should be overread by a physician experienced in reading ECGs before excluding a participant.

- 10. Participants with ANY of the following abnormalities in clinical laboratory tests at screening, as assessed by the study-specific laboratory and confirmed by a single repeat test, if deemed necessary:
 - AST or ALT level $\geq 1.25 \times ULN$;
 - Total bilirubin level $\ge 1.5 \times \text{ULN}$; participants with a history of Gilbert's syndrome may have direct bilirubin measured and would be eligible for this study provided the direct bilirubin level is $\le \text{ULN}$.

Other Exclusion Criteria:

- 11. History of alcohol abuse or binge drinking and/or any other illicit drug use or dependence within 6 months of Screening. Binge drinking is defined as a pattern of 5 (male) and 4 (female) or more alcoholic drinks in about 2 hours. As a general rule, alcohol intake should not exceed 14 units per week (1 unit = 8 ounces (240 mL) beer, 1 ounce (30 mL) of 40% spirit, or 3 ounces (90 mL) of wine).
- 12. Blood donation (excluding plasma donations) of approximately 1 pint (500 mL) or more within 60 days prior to dosing.
- 13. History of sensitivity to heparin or heparin-induced thrombocytopenia.
- 14. Use of tobacco or nicotine-containing products in excess of the equivalent of 5 cigarettes/day or 2 chews of tobacco/day.
- 15. Unwilling or unable to comply with the criteria in the Lifestyle Considerations section of this protocol.
- 16. Investigator site staff directly involved in the conduct of the study and their family members, site staff otherwise supervised by the investigator, and sponsor and sponsor delegate employees directly involved in the conduct of the study and their family members.

5.3. Lifestyle Considerations

The following guidelines are provided:

5.3.1. Contraception

The investigator or their designee, in consultation with the participant, will confirm that the participant is utilizing an appropriate method of contraception for the individual participant and their partner(s) from the permitted list of contraception methods (see Appendix 4, Section 10.4.4) and will confirm that the participant has been instructed in its consistent and correct use. At timepoints indicated in SoA, the investigator or designee will inform the participant of the need to use highly effective contraception consistently and correctly and document the conversation and the participant's affirmation in the participant's chart. Participants need to affirm their consistent and correct use of at least 1 of the selected methods of contraception, considering that their risk for pregnancy may have changed since the last visit.

In addition, the investigator or designee will instruct the participant to call immediately if the selected contraception method is discontinued and document the requirement to use an alternate protocol-specified method, including if the participant will no longer use abstinence as the selected contraception method, or if pregnancy is known or suspected in the participant or partner.

5.3.2. Meals and Dietary Restrictions

- Participants must abstain from all food and drink (except water) at least 4 hours prior to any safety laboratory evaluations, and at least 10 hours prior to the collection of the pre-dose PK and PD biomarker samples on Day 1 (and on Day -1 if relevant for that period), and at least 8 hours prior to PD biomarker collection on Day 2, Day 3, Day 4 (if applicable) and Day 8 ±1 visit (following final dose of study intervention).
- Noncaffeinated drinks (except grapefruit or grapefruit-related citrus fruit juices-see below) may be consumed with meals and the evening snack.
- Dosing under fasted conditions:
 - Following an overnight fast of at least 10 hours, participants will receive study intervention.
 - Water is permitted until 1 hour prior to study intervention administration. Water may be consumed without restriction beginning 1 hour after dosing.
 - No food or drink (other than water) is permitted until lunch approximately 4 hours after dosing and *after* the 4-hour post-dose blood collection samples have been completed.

- Dosing when an effect of a protein-rich meal (eg, MMTT) is investigated, if performed:
 - Following an overnight fast of at least 10 hours, participants will be provided a protein-rich meal as 16 ounces of Ensure Plus® breakfast approximately 20 minutes prior to administration of study intervention. The entire Ensure Plus® meal is to be consumed within 10 minutes with study intervention administered approximately 10 minutes after completion of the meal at 0 hour. There are no water restrictions prior to dosing for participants dosed under fed conditions. Water may be consumed without restriction beginning 1 hour after dosing.
- MMTT on Day -1, if administered:
 - Following an overnight fast of at least 10 hours, participants will be provided a protein-rich meal as 16 ounces of Ensure Plus® breakfast; the timing of administration of the protein-rich meal on Day -1 will be at approximately the same time as planned for administration on Day 1.
- Lunch will be provided approximately 4 hours after dosing and *after* the 4-hour postdose samples (or time-match sample on Day -1 if applicable) have been collected.
- Dinner will be provided approximately 10 hours after dosing and *after* the 10-hour postdose samples (or time-matched sample on Day -1 if applicable) have been collected.
- An evening snack may be permitted. Participants will receive the same evening snack at approximately the same time (± 30 minutes) on Day -1 and Day 1, as well as on any Day -2 if applicable.
- Participants will be provided the same lunch, dinner and snacks on Day -1 when time-matched biomarker assessment is collected and on Day 1 of each period (with or without a MMTT) to strive for as similar food intake as is feasible on these days across periods.
- Participants will be encouraged to consume their entire meals on Day 1 during all periods. In addition, participants will be encouraged to consume their entire evening snack (if applicable) on Day -2 and entire meals on Day -1 if a MMTT is planned for Day -1; if participants do not consume their entire meal on Day -1 where a MMTT is performed, they will be instructed to consume the same amount of food (±10%, with similar uptake of optional snacks) on following Day 1 that they are on Day -1. The approximate percentage of food consumed for these meals should be recorded in the CRF based on visual assessment by the site staff. Participants will not be required to consume all provided food during standard meals on other study days.

- Participants will refrain from consuming red wine, grapefruit, or grapefruit-related citrus fruits (eg, Seville oranges, pomelos, fruit juices) from 7 days prior to the first dose of study intervention until collection of the final PK blood sample.
- While participants are confined, their total daily nutritional composition should be approximately 55% carbohydrate, 30% fat, and 15% protein. The daily caloric intake per participant should not exceed approximately 3200 kcal. However, these guidelines may be adapted to facilitate meal and dietary restrictions required for Day 1 in each period and for Day -1 when time-matched biomarker assessment is collected with or without a MMTT.

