Table 2. Schedule of Activities for PK, PD, Vitals, and ECGs on Day 1 (and Day -1 if Applicable)

Visit Identifier Abbreviations used in this table may be found in Appendix 10.		Day 1, Day -1 (if applicable)											Notes
				Day 1	, Da	ıy -1	(if ap	plic	able)			Applies to Day 1 for Periods 1-4, and for Day -1 when admission occurs on Day -2
Hours Relative to Dosing at 0 hour	-1.0	-0.5	0	0.5	1	1.5	2	3	4	8	10	12	Day 1 activities at time = 0 hour are prior to the dose, except for study intervention administration.
Study intervention administration (Day 1 only)			X										Dosing under fasted or fed conditions (eg, MMTT) is to occur as outlined in Section 5.3.2.
Standardized meal/snack									X		X		See Section 5.3.2 for detailed instruction.
													Participants will be provided the same lunch, dinner and snacks at same times on Day -1 when time-matched biomarker assessment is collected and on Day 1 of each period. If administered on Day -1, MMTT will be administered at the same time as planned for administration on Day 1 (ie, 20 minutes prior to 0 hour).
High protein meal (eg, MMTT)			X										Administered only in periods where food effect is assessed. See Section 5.3.2 for detailed instruction. High protein meal to be provided approximately 20 minutes prior to 0 hours, and consumed within 10 minutes such that study intervention is administer approximately 10 minutes after completion of meal.
Continuous cardiac telemetry (Day 1 only)			X	\rightarrow	\rightarrow	\rightarrow	\rightarrow	\rightarrow	\rightarrow	X			To establish a baseline, telemetry should be recorded for at least a 2-hour interval before dosing in Period 1, either immediately prior to dosing or at some 2-hour continuous interval in the 24 hours prior to dosing when the participant is awake. See Section 8.3.4.1. Assessment on Day 1 initiate at time=0 and continue through 8 hours post dose.
Neurological examination			X				X						Day 1 only. The pre-dose assessment (at time =0 hr) can be completed at any time within 24 hours prior to the dose on Day 1 in each period.
12-Lead ECG (Day 1 only)	X	X	X		X		X	X	X	X		X	Triplicate measures are collected approximately 2-4 minutes apart. See Section 8.3.4 for additional details.
Supine BP and pulse rate (Day 1 only)			X		X		X	X	X	X		X	Single measurement only at 0 hour; triplicate measurement at other timepoints. Triplicate measures are collected approximately 2-4 minutes apart. See Section 8.3.3 for additional details.

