Participants confirming eligibility according to Section 5 will be admitted to the CRU on Day -2 in Period 1 for each cohort and the 1st food period (if applicable) within a cohort. For all other periods (ie, Periods 2-4 except the 1st food period within each cohort), participants will be re-admitted to the CRU on Day -1. For each period in this study, on Day 1, following ≥10-hour overnight fast, participants will receive a single oral dose of PF-07328948 or placebo. Participants have been discharged on Day 3 in Cohort 1 and will be discharged on Day 4, following completion of all scheduled assessments out to 72 hours post-dose in Cohort 2 and optional Cohort 3. Participants may stay in the CRU after completion of Day 4 activities at the discretion of the investigator. In each cohort, a washout interval of at least 7 days will be introduced between subsequent doses. During the washout interval, emerging 24-hour PK and 48-hour safety data will be reviewed and the next dose will be determined. An on-site follow-up visit on Day 8±1 after the final dose and a final follow-up within 28-35 days after the final dose will be scheduled. Final follow-up may be a phone contact or an on-site visit at the discretion of the PI.

Based on the review of emerging safety, tolerability, and PK data (and PD data if available) in Cohorts 1 and 2, the optional third cohort may enroll 8 participants (crossover, placebo-controlled design) to explore additional doses, to repeat a dose, to evaluate split dosing, or to investigate food effects on PK and PD biomarkers.

Dosing will occur in the fasted state for all periods for dose escalation. The effect of a high-protein meal on safety, tolerability, PK exposure, and PD biomarkers may be assessed in at least 1 period within Cohort 2 and/or Cohort 3.

Participants should only need to undergo these time-matched assessments of PD biomarkers on Day -1 once in the fasted state and/or once in the fed state in each cohort, unless there is any uncertainty regarding the reliability of the initial Day -1 assessment. In addition, if thought necessary to achieve study objectives, study intervention may be administered in the fed state (eg, following a high-protein meal) during any of the study periods/cohorts.

The total duration of participation from the screening visit to the telephone follow-up contact will be approximately 14 weeks.

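### On a fasted Day -1 with time-matched biomarker sampling, the amount eaten is not encouraged to be complete, matched to Day 1, or clearly recorded

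*Protocol*

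**What the plan says.** Protocol Section 5.3.2 has two layers of meal control.

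The first concerns what is served, and it covers every time-matched Day -1. Participants are "provided the same lunch, dinner and snacks on Day -1 when time-matched biomarker assessment is collected" and on Day 1 of each period, and the sentence goes on "with or without a MMTT) to strive for as similar food intake as is feasible on these days across periods". Table 2 in Section 1.3 agrees: "Participants will be provided the same lunch, dinner and snacks at same times on Day -1". Section 4.2 describes the same effort to keep meals identical.

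The second concerns what is eaten. Full consumption is encouraged on Day 1 in all periods. On Day -1 the encouragement covers "entire meals on Day -1 if a MMTT is planned for Day -1". The instruction to eat the same amount within ±10% on the following Day 1 applies where an MMTT was performed on Day -1. The CRF entry for approximate percentage consumed refers back to the meals just described. The bullet ends: "Participants will not be required to consume all provided food during standard meals on other study days".

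The Figure 1 notes place time-matched sampling on Day -1 in the first period of each cohort and in the first food-effect period. Section 4.1 says dose escalation is fasted and that participants should need these assessments only "once in the fasted state and/or once in the fed state in each cohort", unless the reliability of the initial Day -1 is in doubt.

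**The concern.** A time-matched Day -1 profile is useful only if it differs from Day 1 in the drug and in little else. The protocol recognises the main confounder in Section 4.2: "As protein intake is known to impact plasma BCAA/BCKA levels". Yet on the fasted Day -1 it fixes what is served, not how much is eaten, while on Day 1 it encourages participants to finish.

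That asymmetry has a direction. If participants respond to the encouragement, they eat more protein on Day 1 than on Day -1. The post-lunch Day -1 value is then too low as a reference, and BCAA/BCKA lowering on Day 1 looks smaller than it is.

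There is a second consequence. Section 4.1 allows Day -1 to be repeated if its reliability is uncertain, but without an intake record a poorly eaten lunch may never come to light.

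PD is among the study purposes in Protocol Section 2.1, and PK/PD modelling is among the reasons for unblinded review in Section 9.4. PD is neither a primary nor a secondary endpoint.

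**Working it through.** **Step 1: which rule covers which day (Protocol 5.3.2 and Table 2).**

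| Provision | Day 1, all periods | Day -1 with MMTT | Fasted time-matched Day -1 |
|---|---|---|---|
| Same menu and meal times | yes | yes | yes |
| Fast of at least 10 h before the pre-dose biomarker sample | yes | yes | yes |
| Encouraged to finish meals | yes | yes | no |
| Amount eaten matched (±10%) on the following Day 1 | not applicable | yes | no |
| Percentage eaten entered in CRF | yes | yes | not named |

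On the literal text the last column belongs to the other study days on which meals need not be finished. The CRF row depends on reading the back-reference as limited to the meals listed just before it. That is the natural reading but not an explicit exclusion.

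**Step 2: are there Day -1 biomarker samples after lunch?** Lunch follows the 4-hour samples. Dinner follows the 10-hour samples, with the addition "or time-matched sample on Day -1 if applicable) have been collected". In Table 2 the PK row is for Day 1 only and has no 10-hour draw, so a 10-hour Day -1 sample is a biomarker sample, taken about 10 − 4 = 6 hours after lunch. Samples up to 4 hours precede lunch on both days and are not affected by that day's lunch.

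**Step 3: illustrative size.** The documents give no figure for this, so there is none to reproduce.

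From Section 5.3.2: about 15% protein and a ceiling of about 3200 kcal/day. Assumed: 4 kcal per gram of protein, lunch as one third of the day, 60% to 80% of lunch eaten on Day -1 against 100% on Day 1, and a lunch-induced BCAA rise of 30% to 60% in proportion to protein eaten.

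- Protein per day: 0.15 × 3200 / 4 = 120 g; at lunch 120 / 3 = 40 g.
- Day -1 shortfall: 40 × 0.20 = 8 g to 40 × 0.40 = 16 g. A 10% tolerance is 40 × 0.10 = 4 g.
- False change from baseline = (1 + rise) / (1 + rise × fraction eaten) − 1.

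| Rise | 60% eaten | 80% eaten | 90% eaten |
|---|---|---|---|
| 30% | 1.30/1.18 − 1 = 10.2% | 1.30/1.24 − 1 = 4.8% | 1.30/1.27 − 1 = 2.4% |
| 60% | 1.60/1.36 − 1 = 17.6% | 1.60/1.48 − 1 = 8.1% | 1.60/1.54 − 1 = 3.9% |

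The first two columns span about 5% to 18%. The last column approximates the edge of the ±10% tolerance. The formula takes the full lunch rise as still present. Six hours after lunch part of it may have gone, so the range is more likely too high than too low for the 10-hour sample.

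**Step 4: is this profile the analysis baseline?** SAP Section 3.4 places the PD baseline definition in Section 3.3.2, which the visible text does not show. The MMRM in SAP Section 5.2.3 uses each participant's average baseline and the deviation of each period's baseline from it. That implies period-specific baselines, because a single reused profile would give zero deviation across fasted periods. Use of the Day -1 profile as the baseline is a reasonable inference from its being time-matched, but it is not confirmed.

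**The case against.** The strongest reply is that food is already well controlled on this day. A reader might infer that meals are unmatched, or protein intake uncontrolled, unless an MMTT is given. The documents do not support that. Menu, meal times and the overnight fast apply with or without an MMTT, and the confinement diet has a composition guideline, though one that may be adapted on these days. Even on Day 1, finishing meals is only encouraged. This part of the reply stands and limits the point to the amount eaten.

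A reader might also infer that one flawed profile is carried into every fasted dose. That cannot be shown: the baseline definition is not visible, the MMRM wording points to period baselines, and Section 4.1 allows a repeat Day -1. If one profile were reused, its error would be constant within a participant and would cancel in that participant's own comparisons of dose with dose or dose with placebo. SAP Section 5.2 also pools placebo over escalation periods. At 3:1 with 8 participants and 4 periods, that is 8 × 4 / 4 = 8 placebo administrations per cohort, or 16 to 24 over two or three cohorts, fewer if fed periods are excluded. Pooling removes an average shift from placebo comparisons. It does not correct change from baseline within a treatment or an individual.

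Finally, the text after the Section 4.2 remark on protein intake is redacted and may contain the sponsor's reasoning. That limits confidence, but it does not alter the operative wording of Section 5.3.2.

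**Conclusion.** The point holds in a narrow form. On a fasted time-matched Day -1, three provisions on the amount eaten do not apply as written (for the CRF entry, on the natural reading), while full consumption is encouraged on Day 1. This works against the protocol's own aim of similar intake on the two days. It could bias post-lunch time-matched changes towards understating BCAA/BCKA lowering, and it leaves the repeat option without intake data.

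The size is not known. The 5% to 18% range is correct arithmetic on assumptions that the documents do not supply, and it presumes that intake errs in one direction. It is tempting to set it against the predicted maximum reductions of 3% (isoleucine) and 4% (ketoisoleucine) at 10 mg in Section 4.3.4 and conclude that low-dose effects would be hidden or reversed. The documents do not support that step. 10 mg is the Cohort 1 starting dose, where the protocol itself expects little target modulation, and Section 4.1 already describes Cohort 1 discharge in the past tense, so no change now reaches it.

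Primary safety and secondary PK endpoints are unaffected, and no hypothesis test depends on this. It is a worthwhile low-cost correction to an exploratory PD measurement.

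**What to change.** For Cohorts 2 and 3, amend the consumption bullet in Protocol Section 5.3.2. In both places where the Day -1 provisions depend on an MMTT, substitute: *on any Day -1 with time-matched biomarker assessment (with or without a MMTT)*. The encouragement to finish meals, the ±10% matching on the following Day 1 and the CRF entry then cover the fasted Day -1 as well.

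Do not make a reduced Day -1 intake the target for later periods. The existing rule reaches only the following Day 1, and carrying it further would conflict with encouraging full meals on Day 1 of all periods. Use the recorded percentage to judge whether the Day -1 profile is reliable or should be repeated under Section 4.1. Some mismatch with later fasted periods may remain, but it will be visible.

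The cost is a wording change and slightly more site recording on about one day per cohort, using a CRF entry that already exists. No visit, sample or procedure is added.
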